4	Total duration of MM-related IP stays	
The total time in days of IP stays with an MM ICD-10 code or treatment for MM, among patients who have at least 1 IP stay (continuous)
	
180 days prior to index date to 1 day prior to index date
 
Step-Up Dosing Period
 
Index date to end of follow-up. Follow-up will be defined two ways to account for gaps in elranatamab use.
 
See Section 9.7.5 for censoring criteria

4	Total MM-related HCRU	
IP, OP, ED, or pharmacy claims with an MM ICD-10 code or treatment for MM (dichotomous)
	
180 days prior to index date to 1 day prior to index date
 
Step-Up Dosing Period

		
IP, OP, ED, or pharmacy claims with an MM ICD-10 code or treatment for MM (continuous)
	
Index date to end of follow-up. Follow-up will be defined two ways to account for gaps in elranatamab use.
 
See Section 9.7.5 for censoring criteria

4	Cost of all-cause IP visits	Cost of IP (non-ED) visits (continuous)	180 days prior to index date to 1 day prior to index date Step-Up Dosing Period Index date to end of follow-up. Follow-up will be defined two ways to account for gaps in elranatamab use. See Section 9.7.5 for censoring criteria
4	Cost of all-cause OP visits	Cost of non-IP/non-ED visits (continuous)	180 days prior to index date to 1 day prior to index date Step-Up Dosing Period Index date to end of follow-up. Follow-up will be defined two ways to account for gaps in elranatamab use. See Section 9.7.5 for censoring criteria

4	Costs of all-cause ED visits	Cost of ED visits (continuous)	180 days prior to index date to 1 day prior to index date Step-Up Dosing Period Index date to end of follow-up. Follow-up will be defined two ways to account for gaps in elranatamab use. See Section 9.7.5 for censoring criteria
4	Cost of all-cause pharmacy claims	Cost of pharmacy claims (continuous)	180 days prior to index date to 1 day prior to index date Step-Up Dosing Period Index date to end of follow-up. Follow-up will be defined two ways to account for gaps in elranatamab use. See Section 9.7.5 for censoring criteria
4	Total cost of all-cause HCRU	Cost of IP, OP, ED, or pharmacy claims (continuous)	180 days prior to index date to 1 day prior to index date Step-Up Dosing Period Index date to end of follow-up. Follow-up will be defined two ways to account for gaps in elranatamab use.

4	Cost of MM-related IP visits	Cost of IP (non-ED) visits with an MM ICD-10 code or treatment for MM (continuous)	180 days prior to index date to 1 day prior to index date Step-Up Dosing Period Index date to end of follow-up. Follow-up will be defined two ways to account for gaps in elranatamab use. See Section 9.7.5 for censoring criteria
		Non-IP/non-ED visits with an MM ICD-10 code or treatment for MM (continuous)	
4	Cost of MM-related OP visits	Cost of ED visits with an MM ICD-10 code or treatment for MM (continuous)	180 days prior to index date to 1 day prior to index date Step-Up Dosing Period Index date to end of follow-up. Follow-up will be defined two ways to account for gaps in elranatamab use. See Section 9.7.4 for censoring criteria
4	Cost of MM-related ED visits	Cost of pharmacy claims with an MM ICD-10 code or treatment for MM (continuous)	180 days prior to index date to 1 day prior to index date Step-Up Dosing Period Index date to end of follow-up. Follow-up will be defined two ways to account for gaps in elranatamab use. See Section 9.7.5 for censoring criteria

4	Cost of MM-related pharmacy claims	Cost of MM-related IP, OP, ED, or pharmacy claim (continuous)	180 days prior to index date to 1 day prior to index date Step-Up Dosing Period Index date to end of follow-up. Follow-up will be defined two ways to account for gaps in elranatamab use. See Section 9.7.5 for censoring criteria
4	Total cost of MM-related HCRU	Cost of MM-related IP, OP, ED, or pharmacy claim (continuous)	180 days prior to index date to 1 day prior to index date Step-Up Dosing Period Index date to end of follow-up. Follow-up will be defined two ways to account for gaps in elranatamab use. See Section 9.7.5 for censoring criteria
Adverse events			
Exploratory Obj 1	CRS ¹	
Medical claim with an ICD-10 code in the IP, non-IP or pharmacy setting for CRS, categorized into the following grades (categorical):
 
Any (all grades and unspecified grade)
 
Grade 1
 
Grade 2
 
Grade 3
	
Index date to end of follow-up, where follow-up will be based on last dose of elranatamab (eg, 14 days after last recorded dose or 90 days after last recorded dose).
 
See Section 9.7.6 for censoring criteria

		Grade 4 Grade 5 If patients have multiple, conflicting grades, then the highest recorded grade will be reported	
Exploratory Obj 1	ICANS ¹	Medical claim with an ICD-10 code in the IP, non-IP or pharmacy setting for CRS, categorized into the following grades (categorical): Any (all grades and unspecified grade) Grade 1 Grade 2 Grade 3 Grade 4 Grade 5 If patients have multiple, conflicting grades, then the highest recorded grade will be reported	Index date to end of follow-up, where follow-up will be based on last dose of elranatamab (eg, 14 days after last recorded dose or 90 days after last recorded dose). See Section 9.7.6 for censoring criteria
Hematologic events			
Exploratory Obj 1	Anemia ¹	Medical claim with an ICD-10 code in the IP, non-IP, or pharmacy setting for anemia or event in the lab table where hemoglobin is <10g/dL (dichotomous)	Index date to end of follow-up, where follow-up will be based on last dose of elranatamab (eg, 14 days after last recorded dose or 90 days after last recorded dose). See Section 9.7.6 for censoring criteria

Exploratory Obj 1	Neutropenia ¹	Medical claim with an ICD-10 code in the IP, non-IP, or pharmacy setting for lymphopenia or event in the lab table where lymphocyte count is < 1,000 per uL (dichotomous)	Index date to end of follow-up, where follow-up will be based on last dose of elranatamab (eg, 14 days after last recorded dose or 90 days after last recorded dose). See Section 9.7.6 for censoring criteria
Exploratory Obj 1	Lymphopenia ¹	Medical claim with an ICD-10 code in the IP, non-IP, or pharmacy setting for lymphopenia or event in the lab table where lymphocyte count is < 1,000 per uL (dichotomous)	Index date to end of follow-up, where follow-up will be based on last dose of elranatamab (eg, 14 days after last recorded dose or 90 days after last recorded dose). See Section 9.7.6 for censoring criteria
Non-hematologic events			
Exploratory Obj 1	Hypogammaglobulinemia ¹	Medical claim with an ICD-10 code in the IP, non-IP, or pharmacy setting for hypogammaglobulinemia or event in the lab table where IGG value is ≤ 400 mg/dL (dichotomous)	Index date to end of follow-up, where follow-up will be based on last dose of elranatamab (eg, 14 days after last recorded dose or 90 days after last recorded dose). See Section 9.7.6 for censoring criteria
Exploratory Obj 1	Hypophosphataemia ¹	Medical claim with an ICD-10 code in the IP, non-IP, or pharmacy setting for hypophosphatemia (dichotomous)	Index date to end of follow-up, where follow-up will be based on last dose of elranatamab (eg, 14 days after last recorded dose or 90 days after last recorded dose). See Section 9.7.6 for censoring criteria

Exploratory Obj 1	Hypokalaemia ¹	Medical claim with an ICD-10 code in the IP, non-IP, or pharmacy setting for hypokalemia or event in the lab table where potassium serum is < 3.0 mmol/L (dichotomous)	Index date to end of follow-up, where follow-up will be based on last dose of elranatamab (eg, 14 days after last recorded dose or 90 days after last recorded dose). See Section 9.7.6 for censoring criteria
Exploratory Obj 1	Hepatotoxicity ¹	Medical claim with an ICD-10 code in the IP, non-IP, or pharmacy setting for hepatotoxicity (dichotomous)	Index date to end of follow-up, where follow-up will be based on last dose of elranatamab (eg, 14 days after last recorded dose or 90 days after last recorded dose). See Section 9.7.5 for censoring criteria
Exploratory Obj 1	Renal failure ²	Medical claim with an ICD-10 code in the IP, non-IP, or pharmacy setting for renal failure (dichotomous)	Index date to end of follow-up, where follow-up will be based on last dose of elranatamab (eg, 14 days after last recorded dose or 90 days after last recorded dose). See Section 9.7.6 for censoring criteria
Exploratory Obj 1	Peripheral neuropathy ¹	Medical claim with an ICD-10 code in the IP, non-IP, or pharmacy setting for peripheral neuropathy (dichotomous)	Index date to end of follow-up, where follow-up will be based on last dose of elranatamab (eg, 14 days after last recorded dose or 90 days after last recorded dose). See Section 9.7.6 for censoring criteria

Exploratory Obj 1	Arthralgia ³	Medical claim with an ICD-10 code in the IP, non-IP, or pharmacy setting for arthralgia (dichotomous)	Index date to end of follow-up, where follow-up will be based on last dose of elranatamab (eg, 14 days after last recorded dose or 90 days after last recorded dose). See Section 9.7.6 for censoring criteria
Hematologic events			
Exploratory Obj 1	Pyrexia ³	Medical claim with an ICD-10 code in the IP, non-IP, or pharmacy setting for pyrexia (dichotomous)	Index date to end of follow-up, where follow-up will be based on last dose of elranatamab (eg, 14 days after last recorded dose or 90 days after last recorded dose). See Section 9.7.6 for censoring criteria
Exploratory Obj 1	Hypotension ³	Medical claim with an ICD-10 code in the IP, non-IP, or pharmacy setting for hypotension (dichotomous)	Index date to end of follow-up, where follow-up will be based on last dose of elranatamab (eg, 14 days after last recorded dose or 90 days after last recorded dose). See Section 9.7.6 for censoring criteria
Exploratory Obj 1	Fatigue ³	Medical claim with an ICD-10 code in the IP, non-IP, or pharmacy setting for nausea or vomiting (dichotomous) Medical claim with an ICD-10 code in the IP, non-IP, or pharmacy setting for diarrhea (dichotomous)	Index date to end of follow-up, where follow-up will be based on last dose of elranatamab (eg, 14 days after last recorded dose or 90 days after last recorded dose).

			See Section 9.7.6 for censoring criteria
Exploratory Obj 1	Nausea or vomiting ³	Medical claim with an ICD-10 code in the IP, non-IP, or pharmacy setting for nausea or vomiting (dichotomous)	Index date to end of follow-up, where follow-up will be based on last dose of elranatamab (eg, 14 days after last recorded dose or 90 days after last recorded dose). See Section 9.7.6 for censoring criteria
Exploratory Obj 1	Diarrhea ³	Medical claim with an ICD-10 code in the IP, non-IP, or pharmacy setting for diarrhea (dichotomous)	Index date to end of follow-up, where follow-up will be based on last dose of elranatamab (eg, 14 days after last recorded dose or 90 days after last recorded dose). See Section 9.7.6 for censoring criteria
Exploratory Obj 1	Angioedema ³	Medical claim with an ICD-10 code in the IP, non-IP, or pharmacy setting for angioedema (dichotomous)	Index date to end of follow-up, where follow-up will be based on last dose of elranatamab (eg, 14 days after last recorded dose or 90 days after last recorded dose). See Section 9.7.6 for censoring criteria
Exploratory Obj 1	Erythema ³	Medical claim with an ICD-10 code in the IP, non-IP, or pharmacy setting for erythema (dichotomous)	Index date to end of follow-up, where follow-up will be based on last dose of elranatamab (eg, 14 days after last recorded dose or 90 days after last recorded dose). See Section 9.7.6 for censoring criteria

Exploratory Obj 1	Muscle spasms ³	Medical claim with an ICD-10 code in the IP, non-IP, or pharmacy setting for muscle spasms (dichotomous)	Index date to end of follow-up, where follow-up will be based on last dose of elranatamab (eg, 14 days after last recorded dose or 90 days after last recorded dose). See Section 9.7.6 for censoring criteria
Exploratory Obj 1	Musculoskeletal pain ³	Medical claim with an ICD-10 code in the IP, non-IP, or pharmacy setting for musculoskeletal pain (dichotomous)	Index date to end of follow-up, where follow-up will be based on last dose of elranatamab (eg, 14 days after last recorded dose or 90 days after last recorded dose). See Section 9.7.6 for censoring criteria
Exploratory Obj 1	COVID-19 ²	Medical claim with an ICD-10 code in the IP, non-IP, or pharmacy setting for COVID-19 (dichotomous)	Index date to end of follow-up, where follow-up will be based on last dose of elranatamab (eg, 14 days after last recorded dose or 90 days after last recorded dose). See Section 9.7.6 for censoring criteria
Infections			
Exploratory Obj 1	Sinusitis	Medical claim with an ICD-10 code in the IP, non-IP, or pharmacy setting for sinusitis (dichotomous)	Index date to end of follow-up, where follow-up will be based on last dose of elranatamab (eg, 14 days after last recorded dose or 90 days after last recorded dose).

			See Section 9.7.6 for censoring criteria
Exploratory Obj 1	Bronchitis	Medical claim with an ICD-10 code in the IP, non-IP, or pharmacy setting for bronchitis (dichotomous)	Index date to end of follow-up, where follow-up will be based on last dose of elranatamab (eg, 14 days after last recorded dose or 90 days after last recorded dose). See Section 9.7.6 for censoring criteria
Exploratory Obj 1 Exploratory Obj 1	Pneumonia ²	Medical claim with an ICD-10 code in the IP, non-IP, or pharmacy setting for pneumonia (dichotomous)	Index date to end of follow-up, where follow-up will be based on last dose of elranatamab (eg, 14 days after last recorded dose or 90 days after last recorded dose). See Section 9.7.6 for censoring criteria
Exploratory Obj 1	Adenoviral pneumonia ²	Medical claim with an ICD-10 code in the IP, non-IP, or pharmacy setting for adenoviral pneumonia (dichotomous)	Index date to end of follow-up, where follow-up will be based on last dose of elranatamab (eg, 14 days after last recorded dose or 90 days after last recorded dose). See Section 9.7.6 for censoring criteria
Exploratory Obj 1	Cytomegaloviral pneumonitis ²	Medical claim with an ICD-10 code in the IP, non-IP, or pharmacy setting for cytomegaloviral pneumonitis (dichotomous)	Index date to end of follow-up, where follow-up will be based on last dose of elranatamab (eg, 14 days after last recorded dose or 90 days after last recorded dose).

			
See Section 9.7.6 for censoring criteria

Exploratory Obj 1	Other pneumonia ²	Medical claim with an ICD-10 code in the IP, non-IP, or pharmacy setting for pneumonia other than adenoviral or cytomegaloviral pneumonia (dichotomous)	
Index date to end of follow-up, where follow-up will be based on last dose of elranatamab (eg, 14 days after last recorded dose or 90 days after last recorded dose).
 
See Section 9.7.6 for censoring criteria

Exploratory Obj 1	Upper respiratory tract infection ²	Medical claim with an ICD-10 code in the IP, non-IP, or pharmacy setting for upper respiratory tract infection (dichotomous)	
Index date to end of follow-up, where follow-up will be based on last dose of elranatamab (eg, 14 days after last recorded dose or 90 days after last recorded dose).
 
See Section 9.7.6 for censoring criteria

Exploratory Obj 1	Sepsis ²	Medical claim with an ICD-10 code in the IP, non-IP, or pharmacy setting for sepsis (dichotomous)	
Index date to end of follow-up, where follow-up will be based on last dose of elranatamab (eg, 14 days after last recorded dose or 90 days after last recorded dose).
 
See Section 9.7.6 for censoring criteria

Exploratory Obj 1 Exploratory Obj 1	Cytomegaloviral infection ²	Medical claim with an ICD-10 code for PJP (dichotomous)	
Index date to end of follow-up, where follow-up will be based on last dose of elranatamab (eg, 14 days after last recorded dose or 90 days after last recorded dose).
 
See Section 9.7.6 for censoring criteria

Exploratory Obj 1	PJP ²	Medical claim with an ICD-10 code for PJP (dichotomous)	Index date to end of follow-up, where follow-up will be based on last dose of elranatamab (eg, 14 days after last recorded dose or 90 days after last recorded dose). See Section 9.7.6 for censoring criteria
Exploratory Obj 1	Hepatitis C ²	Medical claim with an ICD-10 code in the IP, non-IP or pharmacy setting for hepatitis C (dichotomous)	Index date to end of follow-up, where follow-up will be based on last dose of elranatamab (eg, 14 days after last recorded dose or 90 days after last recorded dose). See Section 9.7.6 for censoring criteria
Exploratory Obj 1	Hepatitis B ²	Medical claim with an ICD-10 code in the IP, non-IP or pharmacy setting for hepatitis B (dichotomous)	Index date to end of follow-up, where follow-up will be based on last dose of elranatamab (eg., 14 days after last recorded dose or 90 days after last recorded dose). See Section 9.7.6 for censoring criteria
Exploratory Obj 1	Other infectious hepatitis ²	Medical claim with an ICD-10 code in the IP, non-IP or pharmacy setting for other infectious hepatitis (dichotomous)	Index date to end of follow-up, where follow-up will be based on last dose of elranatamab (eg., 14 days after last recorded dose or 90 days after last recorded dose). See Section 9.7.6 for censoring criteria
Exploratory Obj 1	Helicobacter pylori ²	Medical claim with an ICD-10 code in the IP, non-IP or pharmacy setting for helicobacter pylori (dichotomous)	Index date to end of follow-up, where follow-up will be based on last dose of elranatamab (eg, 14 days after last

			recorded dose or 90 days after last recorded dose). See Section 9.7.6 for censoring criteria
Exploratory Obj 1	Candida esophagitis ²	Medical claim with an ICD-10 code in the IP, non-IP or pharmacy setting for candida esophagitis (dichotomous)	Index date to end of follow-up, where follow-up will be based on last dose of elranatamab (eg, 14 days after last recorded dose or 90 days after last recorded dose). See Section 9.7.6 for censoring criteria
Exploratory Obj 1	Urinary tract infection ²	Medical claim with an ICD-10 code in the IP, non-IP or pharmacy setting for a urinary tract infection (dichotomous)	Index date to end of follow-up, where follow-up will be based on last dose of elranatamab (eg, 14 days after last recorded dose or 90 days after last recorded dose). See Section 9.7.6 for censoring criteria
Exploratory Obj 1	Time to infection onset	Time in days from index date to first infection for the following infections: COVID-19 Sinusitis Bronchitis Adenoviral pneumonia Cytomegaloviral pneumonitis Pneumonia Sepsis Cytomegaloviral infection	Index date until censor See Section 9.7.6 for censoring criteria

		PJP Hepatitis C Hepatitis B Other infectious hepatitis Helicobacter pylori Candida esophagitis Urinary tract infection	
Effectiveness			
Exploratory Obj 2	OS	Time (in months) from index date until date of death (continuous)	Index date until censor See Section 9.7.7 for censoring criteria
Exploratory Obj 2	TTNT/D	Time (in months) from index date until the date of the next treatment (CAR-T, BsABs, bendamustine or belantamab) or death (continuous)	Index date until censor See Section 9.7.7 for censoring criteria

1. Variable will be measured as incident and prevalent. Incident cases have 30-day washout period applied
2. Variable will be measured as incident and prevalent. Incident cases have 60-day washout period applied
3. Variable will be measured as incident and prevalent. Incident cases have 14-day washout period applied

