8. RESEARCH QUESTION AND OBJECTIVES

Research Question: What are the descriptive characteristics, treatment patterns, all cause/MM-related HCRU, safety and effectiveness of elranatamab therapy?

The study objectives are to:

Primary

- **Objective 1:** Describe the demographics, clinical history, and treatment history of patients in the study
- **Objective 2:** Describe the administration and treatment management of elranatamab
- **Objective 3:** Describe all-cause and MM-related HCRU and costs by place of service of patients in the study

Exploratory

- **Exploratory Objective 1:** Describe the tolerability and real-world safety of elranatamab
- **Exploratory Objective 2:** Describe the effectiveness of elranatamab in terms of TTNT/D and OS
- **Exploratory Objective 3:** In a separate cohort, replicate all objectives for patients with the same indication as elranatamab who initiated teclistamab

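### Table 3 gives three of the five MM-related cost variables the wrong definition: OP cost is defined as ED cost, ED cost as pharmacy cost, and pharmacy cost as the total

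*Protocol*

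**What the plan says.** Section 8 makes cost by setting part of primary Objective 3: "Describe all-cause and MM-related HCRU and costs by" place of service. Table 3 in Section 9.3 is where each cost variable is defined.

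In the MM-related cost rows:
- The IP row reads "Cost of IP (non-ED) visits with an MM ICD-10 code or treatment for MM (continuous". An unlabelled line beneath it reads "Non-IP/non-ED visits with an MM ICD-10 code or treatment for MM (continuous".
- The OP row reads "Cost of ED visits with an MM ICD-10 code or treatment for MM (continuous" and, for censoring, "See Section 9.7.4 for censoring criteria".
- The ED row reads "Cost of pharmacy claims with an MM ICD-10 code or treatment for MM (continuous".
- The pharmacy row reads "Cost of MM-related IP, OP, ED, or pharmacy claim (continuous".
- The total row repeats that last definition unchanged.

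The other MM-related cost rows refer to Section 9.7.5 for censoring. For utilization, as opposed to cost, Table 3 has MM-related IP, OP and pharmacy rows but no MM-related ED visit row.

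**The concern.** From the OP row down to the pharmacy row, each label stands beside the definition that belongs to the next one. Section 9.8 says that measures are coded from the definitions in the protocol and that the protocol will be strictly followed. A programmer who did so would produce an OP figure that is ED cost, an ED figure that is pharmacy cost and a pharmacy figure that is the total. A second analyst checking against Table 3 would find the code in agreement with it. The teclistamab cohort replicates all objectives, so it would inherit the same definitions.

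The pointer adds a smaller problem. Section 9.7.4 holds the censoring rule for time to discontinuation. Section 9.7.5 holds the cost periods and a cost-specific censoring rule that includes next treatment.

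**Working it through.** **1. Labels against definitions.** The all-cause cost rows of the same table serve as the template.

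| Row label | All-cause definition | MM-related definition as printed | MM-related match? |
|---|---|---|---|
| IP cost | IP cost | "Cost of IP (non-ED) visits with an MM ICD-10 code or treatment for MM (continuous" | yes |
| OP cost | "Cost of non-IP/non-ED visits (continuous" | "Cost of ED visits with an MM ICD-10 code or treatment for MM (continuous" | no, ED |
| ED cost | ED cost | "Cost of pharmacy claims with an MM ICD-10 code or treatment for MM (continuous" | no, pharmacy |
| Pharmacy cost | pharmacy cost | "Cost of MM-related IP, OP, ED, or pharmacy claim (continuous" | no, total |
| Total cost | all four settings | "Cost of MM-related IP, OP, ED, or pharmacy claim (continuous" | yes |

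All five all-cause rows match their labels. Two of the five MM-related rows match and three do not. The unlabelled OP line under the IP row repeats the definition of the MM-related OP visit count found earlier in Table 3, so even if it were moved to the OP row it would define visits and not cost.

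**2. Whether another section supplies the definitions.** Section 9.7.5 says only that MM-related use means use with a diagnosis code or treatment for MM. Annex 2 defines the IP, OP and ED settings operationally but contains no MM-related cost variable. The meaning can be pieced together from the labels, Section 9.7.5 and Annex 2, but it is not stated by setting outside Table 3.

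**3. Result of coding as printed.** Let I, O, E and P be the true MM-related costs for IP, OP, ED and pharmacy, and T the total. The printed rows return:
- IP row: I (correct)
- OP row: E (error E − O)
- ED row: P (error P − E)
- pharmacy row: T (error T − P)
- total row: T (correct)

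No labelled row returns O. This much needs no assumption about the data.

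If one also assumes that the four settings partition the total (I + O + E + P = T), the four printed setting rows sum to I + E + P + T = (T − O) + T = 2T − O. With s = O/T this is (2 − s)T. For assumed OP shares of 0.70, 0.55 and 0.20 the sum is 1.30T, 1.45T and 1.80T. These shares are illustrations only, since the protocol gives no cost data.

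**4. Whether the partition holds.** Annex 2 does not guarantee it. Its IP definition takes in some events from the non-inpatient table through a different field from the one that identifies OP and ED, so an event could meet two definitions. Its OP and ED definitions both require an outpatient utilization type, so a professional-services event that is not a hospital encounter may meet none.

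**5. The pharmacy rule.** The MM-related pharmacy count row in Table 3 requires a treatment for MM. The displaced pharmacy cost definition accepts either an MM diagnosis code or a treatment for MM. Realigning the rows would still leave count and cost on two different rules.

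**6. The missing row.** Section 9.7.5 lists ED among the settings for both all-cause and MM-related use, and the total MM-related utilization row includes ED. Table 3 goes from MM-related OP visits straight to pharmacy claims.

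**The case against.** The strongest objection is that the table may have been damaged when its text was read from the PDF. Other parts of Table 3 look disturbed too: a vial-size label sits in the utilization block, the neutropenia row carries the lymphopenia definition, and the cytomegaloviral infection row carries the PJP definition. The layout cannot be inspected, so some doubt stands. Three details nevertheless fit an editing error better than a slipped cell: the total definition appears twice, the OP line lacks its cost wording, and the OP row alone among the MM-related cost rows carries the 9.7.4 pointer. The sponsor can settle this by opening its own file.

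A second objection is that nobody would code a variable named pharmacy cost as the total of all settings. The labels are clear, the all-cause rows show the pattern, and Section 9.8 requires review by another analyst or scientist. That stands as an argument that the intent is recoverable. It does not justify leaving the only setting-level definition of a primary-objective outcome wrong.

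A reader might infer that results already delivered are wrong and must be rerun. The documents do not support this. The milestones schedule full results and two refreshes before version 2.0 of 31 July 2025, Annex 1 lists separate table shells, and no output is shown.

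**Conclusion.** As printed, Table 3 misdefines three of the five MM-related cost variables under primary Objective 3. Taken literally, it misassigns three of the four place-of-service costs and reports OP cost nowhere. The IP and total costs are unaffected. The conclusion rests on the text as read from the PDF, with the residual doubt about layout noted above.

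No figure can be put on the error from the documents. A reader might take a sum of, say, 145% of the total as its size, but that needs an assumed OP share of 55% and a partition of settings that Annex 2 does not secure. The 9.7.4 pointer is a minor slip: the same cell speaks of two follow-up definitions, which fits Section 9.7.5. The missing ED visit row is a separate, smaller gap in the same table.

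**What to change.** After checking the source file, correct Table 3 as follows:
- **OP cost:** the cost of MM-related non-IP/non-ED visits.
- **ED cost:** the cost of MM-related ED visits.
- **Pharmacy cost:** the cost of MM-related pharmacy claims.
- **Total:** keep as printed.
- **Unlabelled line under the IP row:** remove it once its content has moved to the OP row with the cost wording restored.
- **Pharmacy rule:** state one rule for an MM-related pharmacy claim and use it for both count and cost, reconciling the two wordings now in the table.
- **Pointer:** send the OP row to Section 9.7.5.
- **New row:** add MM-related ED visits, as a yes/no variable and a count.

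Then confirm which definitions the delivered outputs used, and rerun the MM-related cost tables only if they followed the printed ones. Compare the four settings with the total as a diagnostic. It should not be a pass/fail identity, because the Annex 2 settings may overlap or leave events out.

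The cost is a wording change to one table and a check of existing code. Refresh 4 (20 December 2025) and the final report (28 February 2026) are the last planned deliverables that the corrected table would need to govern.
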